#### 5.2. Treatment Schedule

Crenolanib will be administered for the phase 1 portion as described according to dose levels in Table 6.2. The starting dose is 60 mg TID (dose level 1). Dose escalations will proceed to 80 mg TID (dose level 2) and 100 mg TID (dose level 3) based on DLTs. DLTs will be evaluated during the first cycle of crenolanib treatment. Patients who experience crenolanib related DLTs at dose level 1 will receive a dose reduction to dose level 0 (60 mg BID). Patients who encounter DLTs at dose levels 2 and 3 will receive dose reduction at 1 dose level lower.

## 5.2.1. Arm 1: Crenolanib combined with Standard Salvage Chemotherapy 5.2.1.2 Induction

#### **ARM 1 Induction Dosing Schedule:**

Physician's choice standard salvage chemotherapy regimen:

*Ida/Cytarabine* 

Idarubicin 12 mg/m^2 IV over 1 hr daily on Days 1-3

Cytarabine 1.5 g/m^2 IV continuously over 3 hr on Days 1-4 ( $\leq$  60 yrs) or Days 1-3 (> 60 yrs)

Crenolanib PO starting on Day 5 (+3 day window) continuously

*MEC* + crenolanib

Mitoxantrone 8 mg/m² IV, push on Days 1-5

Etoposide 100 mg/m^2 IV on Days 1-5

Cytarabine 1000 mg/m^2 IV, over 3 hours on Days 1-7

Crenolanib 100 mg TID starting on Day 8 (+3 day window) continuously

FLAG-Ida + crenolanib

Fludarabine 30 mg/m^2 IV on Days 1-5

Cytarabine 2 g/m2 IV over 2 hrs on Days 1-5

G-CSF 300 ug s.c. inj or IV/5ug/kg SC on Day 6, until neutrophil recovery

\*(G-CSF optional, per physician's choice)

Idarubicin 8 mg/m2 IV over 30 min on Days 1-3

Crenolanib 100 mg TID starting on Day 6 (+3 day window) continuously

Crenolanib will be administered continuously until 72 hours prior to next induction cycle or in the case of CR/CRi/CRp, consolidation. If patient achieves a CR/CRi/CRp and will proceed to maintenance following induction, crenolanib does not need to be held 72 hours prior to starting first cycle of maintenance.

Induction cycles can be a minimum of 28 days or a maximum of 60 days (extending a cycle for more than 60 days would require a conversation with the sponsor). A maximum of 2 induction cycles may be given.

If a patient achieves a CR/CRi/CRp after induction cycle 1, this patient will be eligible (at the physician's discretion) to continue to consolidation or maintenance therapy with crenolanib. If a patient is to receive transplant following induction cycle 1, he/she must be discontinued from study treatment prior to transplant.

If a patient has not achieved a CR/CRi/CRp following induction cycle 1, they will not be eligible to start consolidation or maintenance. For a patient who does not achieve CR/CRi/CRp at the end of one induction cycle, a second cycle of induction may be given (per physician's discretion). The same maximum of 60 days duration will be used for the second induction. If a patient achieves a CR/CRi/CRp after induction cycle 2, this patient will be eligible (at the physician's discretion) to continue to consolidation or maintenance therapy with crenolanib. If a patient is to receive transplant following induction cycle 2, he/she must be discontinued from study treatment prior to transplant.

If a patient does not achieve CR/CRi/CRp by the end of the second induction cycle, he/she must be discontinued from crenolanib. Within 30 days of discontinuing crenolanib, prior to new treatment regimen, an end of treatment visit is strongly recommended. At the end of the study, patient's survival status will be assessed.

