#### **MEC**

Crenolanib TID PO administered daily continuously starting on Day 8 (+3 day window). Crenolanib should be discontinued 3 days (72 hours) before the commencement of the next cycle of chemotherapy.

One induction cycle is defined as the first dose of chemotherapy until response can be assessed and treating physician decides on the follow-up regimen. An induction cycle can be a minimum of 28 days and a maximum of 60 days (extending a cycle over 60 days will require a conversation with the sponsor).

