## **SYNOPSIS**

Name of Investigational	Crenolanib besylate (CP-868,596-26)			
Product Title of Study	ase I-II study of Crenolanib Combined with Standard Salvage Chemotherapy and enolanib Combined with 5-Azacitidine in Patients with Acute Myeloid Leukemia th Activating FLT3 Mutations			
Number of Planned Patients	Phase I: Arm 1 (18), Arm 2 (18) Phase II: Arm 1 (26), Arm 2 (26)			
Length of Study	2 years			
Primary Objectives	Phase I:  a. To determine the dose limiting toxicity and maximal tolerated dose of the combination of crenolanib with standard salvage chemotherapy (arm 1) or with 5-azacytidine (arm 2) in patients with refractory/relapsed AML or high-risk MDS with FLT3 mutations.  b. To determine the safety of the combination of crenolanib with standard salvage chemotherapy (arm 1) or with 5-azacytidine (arm 2) in patients with refractory/relapsed AML or high-risk MDS with FLT3 mutations			
	Phase II: To determine the response rate (including the rates of complete remission (CR), CR with incomplete blood count recovery (CRi), and partial remission (PR)) with the combination of crenolanib with standard salvage chemotherapy (arm 1) or with 5-azacytidine (arm 2) in patients with AML or high-risk MDS with activating FLT3 mutations.			
Secondary Objectives	Response rate, Duration of response, PFS, OS, pharmacokinetics and pharmacodynamics of crenolanib with chemotherapy			
Study Design	Open label, dose escalation, two-arm, Phase I-II trialInvestigator to determine treatment assignment			
	Arm 1: crenolanib with standard salvage chemotherapy Arm 2: crenolanib with 5-azacitidine			
	For each arm: Phase I with dose-limiting toxicity (DLT) determination using the Rolling-6 design. Cohort 1 will start with crenolanib at 60 mg TID. Dose escalations to 80 mg TID and 100 mg TID are planned for subsequent cohorts dependent on DLTs.			
	Phase II total of 26 patients in each arm treated at established phase I dose.			
	Enrollment to be simultaneous to each arm.			
Eligibility Criteria	Inclusion Criteria			

- Arm 1: Subjects must have received at least one prior therapy and a maximum of three prior therapies
- Arm 2: Subjects must have received at least one prior therapy and a maximum of three prior therapies. No prior treatment with 5-Azacitidine is allowed in this arm.
- 2. Presence of FLT3 ITD and/or other FLT3 activating mutations
- 3. Extramedullary disease is allowed except for active CNS disease

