#### 2.6. Rationale for Baseline Dose Selection

[figure not shown]
Among 51 AML patients on crenolanib monotherapy, 28 patients have received 100 mg TID and the rest at higher dose of 66 mg/m² TID. Most common adverse events were nausea, vomiting and diarrhea and LFT elevations. As crenolanib will be given in combination with standard salvage chemotherapy or with 5-Azacytidine, a dose escalation schedule will be utilized for this trial. The starting dose of crenolanib at 60 mg TID is 40% less than the dose (100 mg TID) that has been found to be well tolerated in previous phase II studies. If the 60 mg TID is proved to be safe and tolerable in the combination regimen, dose escalations to 80 mg TID and 100 mg TID will be studied. Representative plasma inhibitory activity (PIA) assay from single-agent crenolanib studies showed this dose schedule effectively inhibited the phosphorylated FLT3 (Figure 2.6).

Figure 2.6 Representative PIA result of AML patient samples after single dose crenolanib

To date, 28 AML patients have been treated with 100 mg TID crenolanib. Day 1 pharmacokinetics data is shown in Figure 2.7.

Figure 2.7 Serum concentrations of crenolanib following single dose (100 mg) in AML patients

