#### 3. STUDY DESIGN

This is a Phase I/II, two arm, open label study in FLT3 mutation positive AML of treatment given as either:

Arm 1: crenolanib with standard salvage chemotherapy

Arm 2: crenolanib with 5-azacitidine

Assignment to treatment arm will be determined by the Investigator with enrollment to each arm to occur simultaneously.

Crenolanib will be administered for the phase 1 portion as described according to dose levels in Table 6.2. Phase I will use a rolling-6 design and plan for a total of 18 patients on each arm. The starting dose will be 60 mg TID (dose level 1). Dose escalations will proceed to 80 mg TID (dose level 2) and 100 mg TID (dose level 3) based on DLTs (as defined in section 6.3). DLTs will be evaluated during the first cycle of crenolanib treatment. Patients who experience crenolanib related DLTs at dose level 1 will receive a dose reduction to dose level 0 (60 mg BID). Patients who encounter DLTs at dose levels 2 and 3 will receive dose reduction at 1 dose level lower.

Phase II total of 26 patients in each arm treated at established phase I dose.

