#### 5. TREATMENT PLAN

#### 5.1. General

Patients will be assigned to treatment arm by physician's choice and according to the availability of slots.

The study will enroll patients with relapsed/refractory AML with FLT3 activating mutations. There will be two parallel two arms. In Arm 1 patients will be treated with standard salvage chemotherapy combined with crenolanib. In Arm 2 patients will receive azacitidine combined with crenolanib. Arms 1 and 2 will enroll simultaneously. For both arms, patients will be treated with crenolanib at a starting dose level of 1 (60 mg TID) as defined in the Table 6.2. De-escalation to dose level 0 (60 mg BID) is possible in the event that dose level 1 is found to be too toxic. The dose escalation will proceed independently in each arm. In arm 1 a cycle of induction or consolidation can last for a minimum of 28 days and a maximum of 60 days (extending a cycle for more than 60 days would require a conversation with the sponsor); maintenance cycles will be defined as 28 days. In arm 2 a cycle is defined as 28 days. The first cycle of treatment (in arm 1 and arm 2 independently) will constitute the dose-limiting toxicity (DLT) evaluation period. Study drug will be taken continuously until one of the criteria for study discontinuation is fulfilled.

For each arm of the study, the first 6 patients will be treated at a dose level of 1(60 mg TID). Patients will be entered sequentially to subsequent dose levels, dose level 2 (80 mg TID) and dose level 3 (100 mg TID) after DLTs have been assessed and it is safe to dose escalate. The Rolling-6 design will be used. The Rolling-6 design aims to shorten the duration of Phase I trials by minimizing the time the trial would be closed to accrual for toxicity monitoring. This is achieved by enrolling anywhere from 2 to 6 patients at a dose level without requiring that the DLT status of the patients already assigned to the same dose level are known.

Dose Escalation/De-Escalation Rules in phase I

The following table enumerates all possible scenarios and describes escalation/de-escalation rules that will be applied during dose-finding, separately in each arm:

Table 5.1. Dose escalation/de-escalation rules for the Rolling-6 design

	Dose	e Escalation/De-	Escalation Rules fo	r the Rolling-6 D	Design
				Decision when	n Next Patient is Enrolled
# Pats Enrolled	# Pats with DLTs	# Pats w/o DLT	# Pats with Toxicity Data Pending	Not at the Highest Dose Level	At the Highest Dose Level

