2	0, 1	Any	Any	Stay	
2	2	0	0	De-escalate	
3	0	0, 1, 2	3, 2, 1	Stay	
3	0	3	0	Escalate	

3	1	0, 1, 2	2, 1, 0	Stay	
3	$\geq 2$	Any	Any	De-escalate	
4	0	0, 1, 2, 3	4, 3, 2, 1	Stay	Stay
4	0	4	0	Escalate	Stay
4	1	0, 1, 2, 3	3, 2, 1, 0	Stay	Stay
4	≥ 2	Any	Any	De-escalate	De-escalate
5	0	0, 1, 2, 3, 4	5, 4, 3, 2, 1	Stay	Stay
5	0	5	0	Escalate	Stay
5	1	0, 1, 2, 3, 4	4, 3, 2, 1, 0	Stay	Stay
5	$\geq 2$	Any	Any	De-escalate	De-escalate
6	0	0, 1, 2, 3, 4	6, 5, 4, 3, 2	Suspend	Suspend
6	0	5, 6	1, 0	Escalate	MTD not determined
6	1	0, 1, 2, 3, 4	5, 4, 3, 2, 1	Suspend	Suspend
6	1	5	0	Escalate	MTD not determined
6	≥ 2	Any	Any	De-escalate	De-escalate

The MTD is empirically defined as the highest dose level at which 6 patients have been treated with at most 1 patient experiencing a crenolanib related DLT and the next higher dose level has been determined to be too toxic. The maximum tolerated dose (MTD) may be further defined based on incidence of delayed or cumulative toxicity.

Approximately 88 patients (a maximum of 18 patients in each arm for determination of MTD and 26 patients each arm for phase II portion) will be enrolled in the study. In the dose finding phase I, a maximum of 6 patients at each dose level will be enrolled to establish the proper dose for phase II. As a result, as few as 6 patients and as many as 18 patients can be enrolled in phase I. The recommended dose of crenolanib for testing in the expansion phase will be tentatively identified in the dose escalation phase and will be that which is at or below the MTD, that can be delivered safely in multiple cycles with an acceptable incidence of on-time delivery, and that confers exposure consistent with that needed for efficacy based on the nonclinical models. Once the proper dose has been determined for phase II, an additional 26 patients will be enrolled in each arm.

Table 5.2. Dose levels of crenolanib (applies to both Arms 1 and 2)

Dose Level	Crenolanib mg PO daily during induction
0	60 mg BID
1 (Starting dose)	60 mg TID
2	80 mg TID
3	100 mg TID

Dose adjustments beyond those mentioned in this table or different to the doses specified may be acceptable after discussion with the PI and notification of the sponsor and documentation of the justification recorded in the chart.

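### Arm 1 induction prints crenolanib at a fixed 100 mg TID for MEC and FLAG-Ida, against the 60 mg TID phase I start and the phase II rule of using the established phase I dose

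*Combined protocol and SAP*

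**What the plan says.** **The regimen lines.** Section 5.2.1 lists three physician's-choice induction backbones for Arm 1. For MEC it prints "Crenolanib 100 mg TID starting on Day 8 (+3 day window) continuously". For FLAG-Ida it prints "Crenolanib 100 mg TID starting on Day 6 (+3 day window) continuously". The treatment row of the synopsis carries the same two lines, which makes four in all. The Ida/cytarabine line in the same lists gives no mg figure, and neither does the consolidation line. The MEC box of the study scheme says only "Crenolanib TID PO administered daily continuously starting on" Day 8.

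**The phase I rule.** The synopsis says "Cohort 1 will start with crenolanib at 60 mg TID", with 80 and 100 mg TID to follow depending on DLTs. Section 5.1 says "For each arm of the study, the first 6 patients will be treated at a dose level of 1(60 mg TID"), and admits patients to levels 2 and 3 only after DLTs have been assessed. Sections 3, 5.2, 5.3.2 and 12.1 agree. Table 5.2 heads its list of levels "Crenolanib mg PO daily during induction", which is the treatment phase where the 100 mg lines appear.

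**The phase II rule.** Section 3 says "Phase II total of 26 patients in each arm treated at established phase I dose", and section 5.1 puts that dose at or below the MTD.

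**The reason for escalating.** Section 2.6 says: "As crenolanib will be given in combination with standard salvage chemotherapy or with 5-Azacytidine, a dose escalation schedule will be utilized for this trial". It describes the 60 mg TID start as 40% below a dose found tolerable in earlier studies. The 28 AML patients it reports at 100 mg TID received crenolanib alone.

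**The concern.** The protocol gives two different crenolanib doses for the same patient: an Arm 1 phase I patient in the first cohort whose physician picks MEC or FLAG-Ida. One line in the list has no figure and the next two have one, so a site could take 100 mg TID as a deliberate dose for those two regimens.

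Three things are at stake if that happens.

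- **Patient safety.** The patient would receive the top level before any combination DLT data exist at the lower levels. Obtaining those data first is the reason section 2.6 gives for escalating.
- **Validity of the MTD.** The rule counts DLTs among up to 6 patients at one dose. A nominal level 1 cohort holding both 60 and 100 mg TID patients does not meet that condition, so a decision to escalate or de-escalate from its pooled count would not be valid.
- **Carry-over.** Section 12.1 brings the 6 phase I patients at the MTD into the 32-patient phase II analysis, and section 5.3.2 keeps patients in maintenance on the dose they tolerated earlier. A dosing mix in phase I could reach both.

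**Working it through.** **1. The plan's own figure.** Section 2.6 says 60 mg TID is 40% less than 100 mg TID. Daily doses are 60 × 3 = 180 mg and 100 × 3 = 300 mg, and 1 − 180/300 = 0.40. The figure reproduces.

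**2. Daily dose by level** (Tables 5.2, 6.2 and 12.1), as mg per dose × doses per day, against the printed 300 mg/day:

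| Level | Dose | mg/day | 300 ÷ mg/day | Excess of printed dose |
|---|---|---|---|---|
| 0 | 60 mg BID | 60 × 2 = 120 | 2.50 | 150% |
| 1 (start) | 60 mg TID | 60 × 3 = 180 | 1.67 | 67% |
| 2 | 80 mg TID | 80 × 3 = 240 | 1.25 | 25% |
| 3 | 100 mg TID | 100 × 3 = 300 | 1.00 | 0% |

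The printed dose is two levels above the required start. It agrees with the phase II rule only if level 3 becomes the established dose.

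**3. Patients who should come first.** The earliest escalation in Table 5.1 is at 3 enrolled, none with a DLT, 3 clear and none pending. Over levels 1 and 2 that is 3 × 2 = 6 patients. The maximum is 6 per level, so 6 × 2 = 12. Sections 5.1 and 5.3.2 describe cohorts of 6, which gives 12. Replacement patients are not counted.

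**4. Extent.** There are 2 lines in section 5.2.1 and 2 in the synopsis, 4 in all. They cover 2 of the 3 induction backbones.

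**5. Does any text reconcile the two doses?**

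- Section 5.2, just before the regimen list, sends phase I dosing to Table 6.2 and restates the 60 mg TID start. This supports reading the levels as governing phase I. It does not mention the 100 mg lines.
- Sections 3 and 5.1 supply the phase II dose rule. They too leave the fixed figure in place.
- The note under Table 5.2 allows other doses after discussion with the principal investigator, notice to the sponsor and a charted justification. It concerns adjustments for individual patients and does not authorise a standing starting dose for two regimens.
- Nothing exempts MEC or FLAG-Ida from escalation, confines them to phase II, or says that 100 mg TID has already cleared in Arm 1.

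No sample size, power or significance level depends on this point.

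**The case against.** The strongest reply is that the intended rule is plain. It is stated in the synopsis, sections 3, 5.1, 5.2, 5.3.2 and 12.1 and the dose-level tables, with no exception by backbone, and section 5.2 is the parent of the list containing the stray figures. Phase II has its own rule as well. On this view the defect is a conflicting number, and harm needs a site to follow one line against many. The phase II excesses need a further condition, an established dose below level 3, and the 150% figure needs de-escalation to level 0. The plan gives no probability for any of these.

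There are also safeguards:

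- Section 13.2 has continuous sponsor monitoring of adverse events, a biweekly safety call, review at each dose level, and a limit of 3 patients within 30 days of starting induction 1.
- Site staff write the prescribed dose on the Appendix II diary.
- The diary and PK Form 1 in Appendix V record the dose, so DLTs could be retabulated by dose received.

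Most of this stands. The level-based reading is the better one, the percentages are worst-case ratios and not expected effects, and an undetected mix across a whole cohort is unlikely. However, the safeguards catch or limit a dosing error after the instruction has been read; they do not correct it. The more specific dose, printed in the operative dosing section and again in the synopsis, is the one that departs from the design.

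It is also possible that the MEC and FLAG-Ida lines were written after 100 mg TID had cleared. The documents do not say so, and the current text still starts Arm 1 at 60 mg TID.

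**Conclusion.** The concern holds, and the text must be corrected. Four lines give an unqualified 100 mg TID that contradicts the phase I starting dose and pre-empts the phase II dose decision.

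Followed in cohort 1, they mean 300 instead of 180 mg/day (67% more) on two of three backbones, ahead of the 6 to 12 patients required at levels 1 and 2. The per-level DLT and MTD rule would then not validly apply to that cohort. Followed in phase II, they mean 25%, 67% or 150% above an established dose of 80 mg TID, 60 mg TID or 60 mg BID, and no excess if level 3 is established.

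All of these sizes assume that a regimen line is followed over sections 3, 5.1 and 5.2. The contradiction itself needs no assumption. The escalation design is not in question.

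**What to change.** In section 5.2.1 and the synopsis, replace the 100 mg TID figure for MEC and FLAG-Ida with: *crenolanib PO at the assigned dose level (Table 6.2) in phase I, or at the established phase I dose in phase II*. Use the same wording on the Ida/cytarabine line so that all three backbones read alike. This wording is right whether or not 100 mg TID has since cleared. If it had cleared before MEC and FLAG-Ida were opened, say so explicitly in the protocol.

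If anyone has already been dosed under the 100 mg lines, count their DLTs at the level actually received. The documents report no such patient.

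The cost is four dose lines plus the matching Ida/cytarabine wording, made by written amendment as Appendix I requires. No patients, visits or procedures are added.

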#### 5.2.1.2. Remission Consolidation

#### **ARM 1 Consolidation Dosing Schedule:**

- Idarubicin 8 mg/m^2 IV over 1 hr daily on Days 1-2
- Cytarabine 0.75 g/m^2 IV continuously over 90 min on Days 1-3
- Crenolanib will be given Day 5 (+3 day window) continuously until 72 hours prior to next consolidation cycle. If patient remains in CR/CRi/CRp and will proceed to maintenance, crenolanib does not need to be held 72 hours prior to starting first cycle of maintenance.

Consolidation cycles can be a minimum of 28 days or a maximum of 60 days (extending a cycle for more than 60 days would require a conversation with the sponsor). A maximum of 6 consolidation cycles may be given.

A patient must maintain CR/CRi/CRp to be eligible for a second cycle of consolidation. If a patient is in a CR/CRi/CRp at any time, he/she is eligible for maintenance therapy with crenolanib (per physician's discretion). If a patient is to receive transplant, he/she must be discontinued from study treatment prior to transplant.

If at any time during consolidation a patient relapses or is taken off study for any other reason (such as transplant), an end of treatment visit is strongly recommended. This visit will occur within 30 days of discontinuing crenolanib and prior to new treatment regimen or transplant. At the end of the study, patient's survival status will be assessed.

5.2.1.3. Crenolanib Maintenance

#### **ARM 1 Maintenance Dosing Schedule:**

Patients achieving a remission following induction cycles or patients remaining in remission after consolidation therapy may receive crenolanib for maintenance therapy for up to 365 days. Maintenance therapy will be with single-agent crenolanib and cycles will be defined as 28 days.

If a patient is to receive transplant, he/she must be discontinued from study treatment prior to transplant. If at any time during maintenance a patient relapses or is taken off study for any other reason (such as transplant), an end of treatment visit is strongly recommended. This visit will occur within 30 days of discontinuing crenolanib and prior to new treatment regimen or transplant. At the end of the study, patient's survival status will be assessed.

